9.1.1 Pregnancy

In the unlikely event that a female subject becomes pregnant at any time during the study, the Investigator must notify the Sponsor (Imperial College Healthcare NHS Trust) immediately (within 24 hours) so as to facilitate discussion and implementation of necessary follow-up measures and to enable the Sponsor to submit necessary reports to the ethics committee. The Investigator will be required to follow the subject and pregnancy through delivery (or earlier loss/termination) and report any congenital anomalies or birth defects. Additional information may be requested to meet regulatory reporting requirements.

9.2. Unblinding Procedures

Only in the case of an emergency, when the identity of the study intervention is essential for the clinical management or welfare of the subject, can an Investigator request unblinding of a subject's intervention assignment.

10. STATISTICAL PLAN

10.1. Analysis Populations

This study will include the following analysis populations:

- Randomised Population: all subjects who are assigned an intervention sequence via randomisation in the Intervention Phase
- Intent-to-Treat (ITT) Population: all randomised subjects who receive any study intervention in the Intervention Phase
- Completer Population: all randomised subjects who complete both Visit 1 and 2 in the Intervention Phase
- Per-Protocol Population: all randomised subjects who complete both Visit 1 and 2 in the Intervention Phase and have no major protocol deviations that would confound results
- Safety Population: all subjects who receive any study intervention in the Intervention Phase

Subject allocation to analysis populations, including the review of major protocol deviations and assignment to the Per-Protocol Population, will be based on a blinded review prior to database lock.

10.2. Statistical Methods

10.2.1 General Considerations

All individual subject data for all individual subjects randomised to an intervention sequence will be presented in data listings.

Data collected in this study will be presented using summary tables and data listings. Continuous variables will be summarised using descriptive statistics, such as the number of subjects (n), mean, median, standard deviation (SD), standard error (SE), minimum, and maximum. Categorical variables will be summarised by frequencies and percentages when appropriate. All statistical tests will be two-sided at the 5% significance level, unless otherwise noted.

10.2.2 Demographics and Baseline Characteristics

Subject disposition, demographic and baseline characteristics, prior and concomitant medications, and other background characteristics will be summarised.

10.2.3 Endpoint Analyses

Endpoint analyses (see section 5 for endpoints) will be performed on populations as above. Analyses will be performed based on randomised intervention (Completer and Per-Protocol Populations as appropriate).

The MRI data will be processed and analysed using current best practice methods, which will include (but may not be limited to) application of the General Linear Model (GLM) for neuroimaging data. Robust methods of correcting for multiple comparisons (e.g. permutation testing) will be used for statistical analysis and thresholding of the statistical brain images.

Brain activation patterns will be presented by intervention and analysed by whole-brain and region of interest (including amygdala, thalamus, posterior cingulate cortex and entorhinal region).

Correlations will be explored between brain activation and behavioral data, corrected for visit order as appropriate (including Pearson and Partial Correlation testing).

10.2.4 Safety Analyses

Safety analyses will be performed on the Safety Population; all analyses will be performed based on intervention received. Clinical laboratory results, vital signs, and 12-lead ECG results will be summarised using descriptive statistics (n, mean, SD, SE, median, minimum, and maximum values, as appropriate) by intervention and time point, and all data will be listed.

10.3. Sample Size Justification

The final projected sample size (approximately 30) has been determined by appropriate power calculation and is in line with the recommended n number required for neuroimaging clinical studies to be powered appropriately to be able to observe significant changes in fMRI brain activation patterns (Murphy and Garavan, 2004).

10.3.1 Power calculation

There are no previous functional magnetic resonance imaging (fMRI) studies examining the role of the melanocortin-4 receptor (MC4R) in hypoactive sexual desire disorder (HSDD). However, data from a previous fMRI study (Comninou et al., 2017) examining a similar scenario (kisspeptin hormonal administration effects on fMRI sexual brain activity) can be used to estimate requirements for the current study. The amygdala is an important structure involved in the processing of sexual stimuli in healthy participants as well as patients with HSDD and so is an appropriate reference point. (Woodward et al., 2013). This study shows that kisspeptin enhances blood oxygen level dependent (BOLD) signal change in the amygdala by mean 0.74% and standard deviation 0.38% compared to vehicle (mean 0.48%, standard deviation 0.51%).

We are anticipating a similar response in this study and have performed sample size calculations for the study using these data. With a 5% significance level, and 80% power, and assuming a correlation between Bremelanotide (an MC4R agonist) and vehicle means of 0.4, a sample size of 31 patients is calculated. To allow for natural variation in responses, drop-out and exclusion rate (e.g. a priori head movement > 2mm) of 20%, it is planned to recruit a total of approximately 40 patients to the study.

11. REGULATORY ISSUES

11.1 Ethical Approval

The Principal Investigator will obtain approval from the ... Research Ethics Committee (REC) and Health Research Authority (HRA). The study must also receive confirmation of capacity and capability from each participating NHS Trust before accepting participants into the study or any research activity is carried out. The study will be conducted in accordance with the recommendations for physicians involved in research on human subjects adopted by the 18th World Medical Assembly, Helsinki 1964 and later revisions.

11.2 Confidentiality

The Chief Investigator, [name] is the data custodian. He will preserve the confidentiality of participants taking part in the study under the Data Protection Act 2018. Their data will only be accessed by members of the research team. All samples will be coded by the research team, and these codes will only be accessible to researchers directly involved with the study. Details stored on Imperial College London computers will be password-encrypted and will only be accessed by the researchers involved in the study. Written confidential patient notes will also be kept at Imperial College London, which will contain personal information and medical history of participants. All records will be stored in secure containment for 5 years after the study on the Hammersmith Hospital campus, Imperial College London, under the authority of [name]

If participants are to be enrolled in the study, we will ask their consent to view their medical records. If they are not registered with Imperial College Healthcare NHS Trust (ICHT), a set of ICHT notes will be created. Personal addresses and contact details are required for communication with the participants during the study. This information is held solely for communication between the researchers and participants.

Information held on NHS computers is solely for the purpose of hospital booking, routine sample collection and analysis (e.g. for the screening visit). This information is password-encrypted, in a similar manner to that of other hospital patients. Written confidential patient notes will also be kept, which will contain personal information and medical history of participants.

Personally Identifiable Information (PII) will be entered into Invicro's Patient Information Management System which assigns them a unique six-digit ID. This six-digit ID is used within the Radiology Information System (RIS) for the purposes of verifying the identity of participants immediately prior to the scans. The six-digit participant identification code is the only identifier subsequently used when acquiring the imaging data. The imaging data (and any ancillary data generated) is therefore pseudo-anonymised (code is kept in case of need to un-break blinding). Invicro operates under a highly-secure and enterprise-class computing environment, and fully complies with Good Clinical Practice (GCP) guidelines and Data Protection Act (2018) directives with regard to participant PII. Invicro pseudo-anonymised data will be stored indefinitely. Invicro also holds the study file and consent forms, which are archived indefinitely in a secure off-site document storage facility.

AMAG Pharmaceuticals, Inc. will receive anonymised data relating to this study.

11.3 Indemnity

Imperial College Healthcare NHS Trust holds standard NHS Hospital Indemnity and Insurance cover with NHS resolution for NHS Trusts in England, which apply to this study.

Separate insurance is held by Invicro for the conduct at their site.

11.4 Funding

AMAG Pharmaceuticals Inc are funding this study. Participants will receive £150 per completed study visit to cover expenses including travel costs, time off work and lost earnings, in keeping with NIHR guidelines.

11.5 Audits

The study may be subject to inspection and audit by Imperial College Healthcare NHS Trust under their remit as Sponsor, the Study Coordination Centre and other regulatory bodies to ensure adherence to GCP.

11.6 Sample storage

At the end of the study, the data will be kept in locked storage in the Department of Investigative Medicine on the Hammersmith Hospital campus, Imperial College London, under the authority of [name]. On a day-to-day basis, data will be managed by the department's senior administrative manager. Only the researchers will have access to the data. Samples will be stored for 5 years.

Appendix A: STUDY FLOWCHART

Variables	Screening (Visit 0)	Intervention phase (Visit 1)	Intervention Phase (Visit 2)
Informed Consent Form (ICF)	X		
Review inclusion/exclusion criteria	X	X	X
Demographics	X		
Medical, social and sexual history	X		
Review medications	X	X	X
Perform diagnostic screening for HSDD	X		
Perform baseline screening questionnaires: PHQ-9, BSS, FSFI, FSDS-DAO, MMAS	X		
Vital signs	X	X	X
12-lead ECG	X		
Urine pregnancy test	X	X	X
Physical exam	X	X	X
Clinical laboratory tests	X	X	X
Randomisation		X	
Continued eligibility assessment		X	X
Administer intervention BMT/placebo		X	X
fMRI & behavioral potentiometer (including handheld device and questionnaires such as VAS, STAI Y1 and Y2, SADI, PANAS, D2 Test of Attention)		X	X
Review adverse events		X	X

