1.3.1 Pharmacokinetics of BMT

In two studies (PT-141-56 and PT-141-54), BMT absorption was rapid and complete after SC injection with the typical T_{max} occurring at approximately 60 minutes in the plasma; the half-life ($t_{1/2}$) is approximately 2 to 3 hours. After an SC dose of 1.75 mg BMT, the typical maximum concentration (C_{max}) in the plasma was 77.1 ng/mL. Human material studies showed that BMT had low binding to human plasma protein. The proposed biotransformation in humans is the breakdown of BMT into its constitutive amino acids through hydrolysis of the amide bonds. BMT and its breakdown products are predominantly renally cleared and excreted in the urine (64.8%); there is also some hepatic clearance but no BMT is detected in faeces.

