3.1. General Design

This is a randomised, double-blind, placebo-controlled, two-way crossover physiological study. It is designed to evaluate the effects of MC4R activation on brain activity patterns and behavioral psychometric measures of sexual arousal during visual erotic stimuli in approximately 40 right-handed, heterosexual, premenopausal women ≥ 18 years of age with HSDD (≥ 6 -month duration) (see power calculation for determination of sample size).

The study will consist of two Phases: Screening & Intervention (MC4R agonist (BMT) or placebo). (Figure 1).

- Screening Phase (Visit 0).
- During the Intervention Phase, eligible subjects will be randomised (1:1) to one of two intervention sequences (AB or BA). Subjects will receive a single dose of BMT or matching placebo, administered SC, during each of the two Intervention Phases (Visit 1 and Visit 2) based on the randomisation intervention sequence they are assigned. The crossover design, which allows subjects to serve as their own control, will minimise inter-participant variability. Participants will return for Visit 2 in the same phase of the menstrual cycle of a subsequent month.
- Subjects who are randomised to intervention sequence AB will receive BMT 1.75 mg SC (Intervention A) during Intervention Phase 1 (Visit 1) and will receive placebo (Intervention B) during Intervention Phase 2 (Visit 2). Subjects who are randomised to intervention sequence BA will receive placebo (Intervention B) during Intervention Phase 1 (Visit 1) and will receive BMT 1.75 mg SC (Intervention A) during Intervention Phase 2 (Visit 2). Subjects will remain at the study centre for approximately seven hours during each of the Intervention Phases. Subjects may be required to remain at the study centre longer at the discretion of the Investigator.

Figure 1: Study Schematic

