4.1. Inclusion Criteria

A subject will be eligible for enrollment in the study if all the following criteria apply:

1. Heterosexual premenopausal females \geq 18 years of age with normal menstrual cycles \leq 35 days.
2. Right hand dominant.
3. Body mass index (BMI) 18-35kg/m².
4. Currently in a relationship with a male partner and the relationship has been stable for at least 6 months before screening.
5. Male sexual partner classified as “not impotent” on the Massachusetts Male Aging Study (MMAS) (O’Donnell et al., 2004) single-question assessment of erectile dysfunction.
6. In the subject’s opinion, previously experienced “normal sexual function,” defined as a normal level of desire at some point in the past, for a period of at least 2 years.
7. For all subjects of childbearing potential who are sexually active, agree to routinely use adequate non-hormonal contraception from randomisation throughout the duration of the study and for 30 days after.
8. For at least 6 months before Screening, met the diagnostic criteria for HSDD according to the Diagnostic Screening Guide for HSDD (**Appendix B**), including categorisation of the sexual dysfunction as both acquired (versus lifelong) and generalised (versus situational).
9. All of the following at Screening:
 - a. Patient Health Questionnaire (PHQ-9) (Kroenke et al., 2001) total score is <10.
 - b. PHQ-9 score for Question 9 is 0.

- a. Either Female Sexual Function Index (FSFI) (**Appendix C**) total score ≤ 26 if diagnosed with HSDD (with or without symptoms of decreased arousal) or subjects diagnosed with HSDD only (without symptoms of decreased arousal), FSFI desire domain score of ≤ 5 (regardless of total FSFI score).
- b. Female Sexual Distress Scale - Desire/Arousal/Orgasm (FSDS-DAO) (**Appendix D**) total score is > 18 .

10. Capable of understanding and complying with the protocol requirements and available for the duration of the study.
11. Subjects must have prior experience in viewing sexually explicit material.

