7.2.1 Intervention Phase (Visits 1 and 2)

Visit 1

Visit 1 will occur after Screening (Visit 0), on **day 1-7** of the menstrual cycle. Subjects will be randomised and the following procedures will be performed:

- On arrival
 - review and confirm study eligibility
 - perform vital signs assessment (systolic and diastolic BP, heart rate, temperature)
 - perform symptom-driven physical examination
 - collect blood and urine for clinical laboratory tests (haematology, serum chemistry, urinalysis)
 - perform urine pregnancy test
 - review concomitant medications
 - MRI safety questionnaire
- Prior to intervention
 - remove intervention autoinjector from assigned study kit; warm to room temperature
 - collect arousal/psychometric data using behavioral potentiometer (including the Visual Analogue Scale (VAS), the State-Trait Anxiety Inventory (STAI Y1 and

Y2), the Sexual Arousal and Desire Inventory (SADI) and the Positive and Negative Affect Schedule (PANAS) at the end of scanning component of session (see Appendices E to I).

- Post-intervention assessments:
 - administer intervention based on randomisation assignment
 - collect blood at time-points: -15, 0 (SC injection), 15, 45, 60, 75, 90, 120, 150, 180, 210, 240, 270, 300 (14 timepoints total). A maximum of 12ml will be taken at each time-point. The total volume of blood collected over both study visits will not exceed 340ml.
 - During SS1:
 - perform fMRI in accordance with Imaging Manual instructions (including functional MRI scan (commencing t=45mins) and anatomical MRI scan)
 - Exposure to visual erotic stimuli as well as other tasks designed to elicit brain responses related to emotional, sensory, or cognitive functions.
 - collect psychometric data using behavioral potentiometer alongside session (arousal handheld device in scanner and psychometric/behavioral potentiometer questionnaires including the Visual Analogue Scale (VAS), the State-Trait Anxiety Inventory (STAI Y2), the Sexual Arousal and Desire Inventory (SADI) and the Positive and Negative Affect Schedule (PANAS) at the end of scanning component of session (see Appendices E to I).
 - During SS2:
 - perform fMRI (and anatomical scan) in accordance with Imaging Manual instructions (commencing t=240mins)
 - Exposure to stimuli as per SS1.

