 - collect psychometric data using behavioral potentiometer alongside session (arousal handheld device in scanner and psychometric/behavioral potentiometer questionnaires including the Visual Analogue Scale (VAS), the State-Trait Anxiety Inventory (STAI Y2), the Sexual Arousal and Desire Inventory (SADI), the Positive and Negative Affect Schedule (PANAS) and the D2 Test of Attention at the end of scanning component of session (see Appendices E to I).

Visit 2

This will occur on **day 1-7** of a subsequent menstrual cycle, to allow for the study to be carried out in the same part of the menstrual cycle on each visit.

The following procedures will be performed:

- On arrival
 - As described for Visit 1
- Prior to intervention
 - As described for Visit 1

- Post-intervention assessments
 - As described for Visit 1

Follow-up

Participants will be sent a short questionnaire 24 hours after the study to assess the perceived duration of effect of BMT (see Appendix J).

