APPENDIX J: Follow-up Questionnaire

1. Did you feel an increase in sexual desire after administration of study drug? YES/NO
2. If yes, how long after study drug administration did the increase in sexual desire last?

0-2 hrs
>2-4 hrs
>4-8 hrs
>8-12 hrs
>12-18 hrs
>18-24 hrs

Thank you

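### Adverse events are not solicited after discharge from Visit 2, so scheduled observation after a dose lasts hours in the second period and possibly weeks in the first

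*Combined protocol and SAP*

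**What the plan says.** Section 5.4 lists AE incidence first among the safety measures. In Appendix A the row "Review adverse events" is marked at Visit 1 and Visit 2, and the table ends with Visit 2.

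On the day of dosing, section 3.1 states: "Subjects will remain at the study centre for approximately seven hours during each of the Intervention Phases". The investigator may extend the stay. Section 7.2.1 puts the last blood sample 300 minutes after injection and starts the second scan at 240 minutes.

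Visit 2 falls on day 1-7 "of a subsequent menstrual cycle, to allow for the study to be carried out in the same part of the menstrual cycle". Inclusion criterion 1 caps cycle length at 35 days and gives no lower limit.

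After discharge, 7.2.1 provides one contact: "Participants will be sent a short questionnaire 24 hours after the study to assess the perceived duration of effect of BMT". The form in Appendix J has two items. The first begins "Did you feel an increase in sexual desire after administration of study drug", and the second asks how long any increase lasted, in bands up to 24 hours. Neither asks about symptoms.

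Section 9.1 makes the reporting of all AEs and SAEs mandatory while the study runs, and provides for fortnightly safety meetings. It sets no length for the post-dose window and no AE contact after the last dose. Section 10.2.4 analyses safety by intervention received. It names laboratory results, vital signs and ECG for summary, and gives no window or attribution rule for AEs.

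**The concern.** Every participant receives one dose at each visit. After a Visit 1 dose she is seen again, and AE review is marked at that second visit. After a Visit 2 dose nobody is scheduled to ask her about symptoms once she leaves. Following the plan exactly, what is learned about the hours and days after a dose depends on the period in which it was given.

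Two things are at stake. First, AEs that begin or continue after the last discharge enter the data only if the participant volunteers them. Second, an AE incidence by intervention would pool doses observed for hours with doses that may have been observed for weeks, so it could not be read as a rate per dose over any stated time.

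The gap is easy to see in Appendix J itself: the plan asks about increased desire over the 24 hours after dosing, but asks nothing about unwanted effects over the same 24 hours.

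**Working it through.** The plan states no figure for AE observation time, so there is none to reproduce. The windows follow from the visit schedule.

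**Doses affected.** Allocation is 1:1 to AB or BA with about 40 women (3.1). Visit 2 carries BMT in sequence BA and placebo in sequence AB.
- BMT doses given at Visit 2: 40 / 2 = about 20 of 40.
- Placebo doses given at Visit 2: 40 / 2 = about 20 of 40.
- With 30 completers, 15 of 30 for each.

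**Window after a Visit 2 dose.** The lower bound is the last sample, 300 / 60 = 5 h. The upper bound is the whole stay of about 7 h, which includes pre-dose procedures. The window is therefore 5 to under 7 h, unless the investigator extends the stay.

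**Window after a Visit 1 dose.** Let L be the cycle length, with Visit 1 on day a and Visit 2 on day b of the next cycle, both between 1 and 7. The interval is L + b - a, which runs from L - 6 to L + 6 days.

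| L (days) | Interval (days) |
|---|---|
| 21 (assumed minimum) | 15 to 27 |
| 28 | 22 to 34 |
| 35 (protocol maximum) | 29 to 41 |

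The overall range is 15 to 41 days, and longer if a later cycle is used. It counts as AE observation only if the Visit 2 review asks about the time since Visit 1, which the plan does not state. A woman who never returns has only the hours before discharge after her Visit 1 dose as well.

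**Ratio of the windows.** Smallest: 15 × 24 / 7 = 51. Largest: 41 × 24 / 5 = 197. That is roughly 50-fold to 200-fold.

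**Drug remaining at the end of observation.** Section 1.3.1 gives Tmax of about 60 minutes, Cmax of 77.1 ng/mL and a half-life that "is approximately 2 to 3 hours". Assuming mono-exponential decline from the peak, the fraction of Cmax at time t is 0.5^((t - 1) / half-life), with t in hours.
- At 5 h (4 h after peak): 0.5^(4/2) = 0.25 and 0.5^(4/3) = 0.397, so about 25-40% of Cmax, or 19.3 to 30.6 ng/mL.
- At 7 h (6 h after peak): 0.5^(6/2) = 0.125 and 0.5^(6/3) = 0.25, so about 12-25% of Cmax, or 9.6 to 19.3 ng/mL.

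**Balance between treatments.** Take 28 days (672 h) for a Visit 1 dose and 7 h for a Visit 2 dose.
- Split 20/20: BMT 20 × 672 + 20 × 7 = 13,580 h; placebo is the same.
- Split 24 AB / 16 BA, for illustration: BMT 24 × 672 + 16 × 7 = 16,240 h; placebo 16 × 672 + 24 × 7 = 10,920 h.

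Balanced sequences give equal totals. Unequal sequences or dropout would not.

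**The case against.** The strongest reply is that the imbalance is by period and not by treatment. A reader might infer that BMT is under-observed relative to placebo and that the comparison is biased. The documents do not support that: placebo doses have the same mix of long and short windows, and with balanced sequences and completion the difference has no bias in expectation. This objection stands.

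Four further limits also stand.
- A reader might infer that late events cannot be reported at all. Section 9.1 requires all AEs to be recorded and reported during the study, and nothing bars spontaneous reports. The contact and consent pages are not in this copy, so any instructions to participants cannot be judged. What is missing is solicited collection.
- A reader might infer that weeks of background events are charged to the Visit 1 product. No section says so; 10.2.4 simply has no attribution rule.
- A reader might apply the nausea rate per injection in 1.3.3 to the Visit 2 doses and call the result unmonitored nausea. That rate counts any nausea, not nausea present after discharge, and the documents give no onset or duration data to convert it. Nausea is also rated on site by visual analogue scale before dosing and with each scanning session (7.2.1, Appendix E).
- Residual drug does not prove that events are missed. The one effect with stated timing, the blood pressure rise, peaked at about 2 hours and had gone within 4 hours (1.3.3), inside the stay.

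Safety is also neither a primary nor a secondary objective, and the fMRI endpoint is untouched. That limits the weight of the point. None of these arguments supplies a symptom enquiry after discharge from Visit 2.

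**Conclusion.** The point holds as a gap in solicited AE collection. For about half of BMT doses and half of placebo doses, scheduled observation ends about 5 to under 7 hours after injection, when an estimated 12-40% of peak concentration remains. The other half have a further review about 15 to 41 days later. The consequence is under-ascertainment after the second dose, and an incidence by intervention that mixes unequal windows. A biased BMT-placebo contrast does not follow unless sequences or completion become unbalanced.

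The size rests on four assumptions: a 21-day minimum cycle, return in the next cycle, a Visit 2 review that covers the interval, and mono-exponential decline from the stated Tmax. The gap itself rests on none of them; it can be read directly from Appendix A, 7.2.1 and Appendix J. It is a cheap improvement and does not threaten the study's main conclusion.

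**What to change.** - **Appendix J:** add an item on new or continuing symptoms since leaving the centre, with time of onset and time of resolution.
- **7.2.1:** state that the questionnaire is sent 24 hours after each of Visits 1 and 2. The present wording does not make clear that it follows both.
- **Appendix A:** add a column for this contact and mark the AE row in it.
- **10.2.4:** tabulate AEs by intervention over a common window from dose to the 24-hour contact, and list later events separately.

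The cost is a small extra burden on participants and a little more data handling, with no additional visit or procedure. The remedy is partial: events beginning more than 24 hours after the Visit 2 dose would still depend on spontaneous report. The common window would, however, be the same length for every dose, including doses given to women who do not return for Visit 2.
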